1. BACKGROUND, RATIONALE AND OBJECTIVES

1.1 Background

Abdominal aortic aneurysm (AAA) is a major health issue and ruptured AAA a common cause of death in Europe and North America. In Sweden 700-1000 annual deaths are attributed to AAA. To prevent rupture, early detection and preventive surgical repair in selected individuals is recommended. AAA screening programs are already implemented in the UK, Sweden and the USA. Most screening detected AAAs are, however, small (diameter 30-54 mm) and are under surveillance until expansion to the threshold for elective surgical repair; i.e. diameter ≥55 mm for men and ≥50 mm for women. Presently approximately 15,000 men and women are being monitored for small AAAs in Sweden, of whom 70% eventually will require surgical repair. In 2015, ~1200 AAA repairs were performed in Sweden at a cost of ~30 million Euros (Swedvasc 2016). AAA repair is associated with significant mortality (1-5%), perioperative complications (up to 20%), cost (~25,000 Euros/patient) and need for life-long post-operative follow-up, imaging and repeat surgery (in ~20% of cases) (Mani 2009, Mani 2010, Mani 2013).

A key limitation of contemporary treatment strategies of AAA is the lack of therapy directed at small AAA (Wanhainen 2019). Although surgical repair is an effective treatment for large AAA, several large trials (Powell JT 2007, UKSAT 2002, Lederle 2002, Cao 2011) have shown that early surgery of small AAA does not reduce mortality. Given that AAA diameter is the strongest predictor for rupture and the natural course for AAA is continued expansion, a mean to reduce AAA growth rate would be highly beneficial. Commonly used cardiovascular drugs, such as anti-platelet drugs, statins, angiotensin converting enzyme inhibitors and beta-blockers have not been shown to slow AAA growth in cohort studies (Ferguson 2010, Twine 2011). Previous interventional trials with therapy directed at AAA growth reduction include antibiotics, mast cell inhibitors, beta-blockers, platelet inhibitors, and angiotensin converting enzyme blockers, with trials of stem cells and cyclosporine under way. These trials have all been either small, with negative results or had unacceptable side effects (Meijer 2013, Sillesen 2015, PATI 2002, Golledge 2017, Rughani 2012).

Risk factors for AAA often mimic those of arteriosclerosis, with the notable exception of diabetes mellitus. Several large trials have shown that people with diabetes are less likely to develop AAA and when they do; the AAA expands slower and is less likely to rupture (Xiong 2016, Kent 2010, Lederle 1997, Golledge 2008, Thomson 2013, De Rango 2012, Takagi 2016, Theivacumar 2014). However, in 2016 a study of 58 patients with diabetes reported that the drug metformin, the world's most widely used drug for type II diabetes, was associated with reduced AAA growth (Fujimura 2016). Following this, a cohort study of 1.2 million patients with diabetes, reported that metformin prescription was associated with a 36%

reduced risk of developing an AAA (Hsu 2016) and in a cohort of 1755 AAA patients a 36-76% slower AAA growth rate were reported in patients with diabetes and metformin prescription, but not those without (Golledge 2017). A similar finding was made in a cohort of 13,834 American veterans with AAA and diabetes where metformin was independently associated with reduced growth rates of AAA of different sizes (Itoga 2018).

Metformin may reduce AAA growth by inhibiting key pathological mechanisms implicated in AAA, including inflammation and extracellular matrix remodeling. Two different rodent models of AAA have found that metformin may reduce AAA growth in euglycemic animals (Fujimura 2016, Vasamsetti 2015). These studies suggest that metformin may reduce AAA growth by reducing aortic inflammation, elastin degradation, smooth muscle cell depletion and monocyte infiltration independent of glucose levels.

In house data (in manuscript) from a cohort of 526 patents under surveillance for small AAA support these findings with a reduced AAA growth rate and altered cytokine expression in patients prescribed metformin. In a connected experimental animal study, metformin was also shown to inhibit AAA formation, improve endothelial vasomotor function and reduce proinflammatory gene expression in euglycemic mice.

Metformin is a well-established first-line treatment of type II diabetes. It acts primarily by reducing blood glucose levels by inhibiting hepatic glucose production and increase insulin sensitivity. It is cheap, safe and able to reduce micro- and macrovascular complications and overall death (UKPDS 1998, Holman 2008, Griffin 2017). This has prompted several large trials of metformin given to persons without diabetes (DPPRG 2002, Syngelaki 2016) showing that metformin is safe and highly tolerable in variable patient groups.

Metformin is available as a generic drug at low cost. It is generally well tolerated, with few serious side effects. Gastro intestinal problems may occur primarily in the run-in phase. This is usually mitigated by taking metformin with a meal and increasing the dose stepwise over a course of several weeks to the desired level.

As metformin is a generic drug there is no commercial interest in exploring its potential as a drug to reduce AAA growth, necessitating an academically driven trial.

The rationale for this randomised controlled trial is to investigate whether treatment with metformin inhibits growth of small AAAs.

1.2 Objectives

The proposed multi-centre population-based open-label randomized controlled trial with blinded outcome assessment will examine if metformin slows AAA growth in patients with small AAAs who do not have diabetes

1.2.1 Primary objective

To examine if up to 2g metformin administered daily over a five-year period slows AAA growth measured as computed tomography (CT) imaging assessed AAA diameter in patients with small AAAs who do not have diabetes.

An interim STOP/GO analysis will be performed after two-years of treatment.

1.2.2 Secondary objectives

To examine if metformin limits increase in; a) CT-assessed AAA volume; b) ultrasound assessed AAA diameter; c) improves health-related quality of life; d) reduces the need for surgery (diameter ≥55mm) or rupture; and e) represents a cost-effective treatment to reduce the need for AAA surgery.

1.2.3 Exploratory objectives

To examine; a) if there is a dose or time related response of metformin regarding the primary or secondary endpoints; and b) if metformin favourably modifies circulating inflammation and matrix remodelling biomarkers; or c) affects perivascular adipose tissue.

1.2.4 Safety objective

To determine adverse events; primarily related to known side effects of metformin and possible unexpected effects on AAA, related to metformin treatment after two and five years.

2. STUDY PLAN AND PROCEDURES

2.1 Study design

The MAAAGI-trial is a population-based multi-center, prospective, parallel group, randomized, open label trial with blinded outcome assessment to assess if metformin up to 2g daily over a five-year period will reduce AAA growth in patients who do not have diabetes.

Patients will be recruited from a cohort of patients with diagnosed AAA at the following seven Swedish sites; 1) Uppsala University hospital, Uppsala, 2), Skåne University hospital, Malmö, 3) Gävle county hospital, Gävle, 4) Västerås county hospital, Västerås. 5) Karlstad county hospital, Karlstad 6) Falun county hospital, Falun, and 7) Umeå University Hospital, Umeå.

The patients should have a maximum aortic diameter of 30-49mm for men and 30-44mm for women, not have diabetes and be expected to tolerate metformin.

A total of 500 patients with AAA will be included in the study, 250 in each study arm. Patients will be randomised to metformin or standard care in a 1:1 ratio.

The patients are scheduled for one enrolment visit, eight study visits and ten phone contacts for those randomized to metformin (three to support titration of study drug) and seven phone contacts for those randomized to standard care. The study visits will take place at the vascular laboratory at the respective surgical departments for clinical examination and blood sampling and at the CT units at the radiology departments where CT-imaging will be performed.

After a run in phase to support titration of metformin, visits and phone contacts are scheduled to alternate every three months until 24 months and twice yearly thereafter. CT imaging and AAA US will be performed at baseline, 24 months and end of study, as well as if necessary according to clinical routine. Study drug will start at baseline and continue through completion.

End of study is defined as 1) study completion at 60 months, or 2) discontinuation from study before that for any reason, for example due to AAA repair or patients will.

When all patients have completed the 24-month follow-up (including imaging) an interim analysis will be performed to assess for efficacy and safety; if there is no trend towards a positive effect or signs of a harmful effect of metformin, the study will be stopped at this phase.

The study will be performed in accordance with the ethically acceptable principles that have their origin in the Declaration of Helsinki and according to national legislations and international regulations. In addition, the study will be performed in accordance with this study protocol.

	Enrolment	Baseline/ Visit 1	Phone 2*	Phone 3*	Phone 4*	Phone 5	Visit 6	Phone 7	Visit 8	Phone 9	Visit 10	Phone 11	Visit 12	Phone 13	Visit 14	Phone 15	Visit 16	Phone 17	Completion
Visit window		$Day 0^{l}$	2 weeks	4 weeks	6 weeks	3 months	6 months	9 months	12 months	15 months	18 months	21 months	24 months	30 months	36 months	42 months	48 months	54 months	60 months
Informed consent	X																		
In- & exclusion criteria	x																		
Demographics ²	x																		
Smoking status	x						X		X		X		x		X		Х		X
Medical history	x																		
Current medication	x								X				x		X		Х		X
Physical examination ³	x												x						X
Vital signs ⁴	x						X		X		X		x		X		x		X
QoL questionnaires ⁵	x												x						X
CT scan		x											x						X
Blood samples ⁶	x								X				x		X		X		X
Randomisation		x																	
Ultrasound ⁷	x												x						X
Drug prescription*		x					X		X		X		x		X		Х		
Drug accountability*			X	X	X	X	X	X	X	X	X	X	X	X	X	X	х	X	X
Target dose of study drug*		X	X	X	X	X	X	X	X	X	X	X	X	X	X	X	х	X	
AE registration	X	X	X	X	X	X	X	X	X	X	X	X	X	X	X	X	х	X	х
SAE registration	x	x	x	x	x	X	X	X	x	X	X	x	x	x	x	X	x	x	X

Table 1. Overview of study activities. Phone 2-5 are to be performed +/- 5 days from target date and the remaining activities +/- 4 weeks from target date.

¹ Within four weeks of enrollment

² Demographics includes date of birth, sex and ethnicity

³ Physical examination includes cardio-pulmonary status and general appearance

⁴ Vital signs include blood pressure, heart rate, height (only at enrollment) and body weight

⁵ EQ-5D and RAND-36

⁶ Safety lab at all sites and blood samples for biobank at Uppsala and Malmö

⁷ Final Ultrasound +/- one week from CT scan

^{*} For those randomized to metformin only, see item 4.1.1 below

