4.2 Withdrawal from study

Patients may be discontinued from the study at any time, at the discretion of the investigator.

Patients are free to discontinue their participation in the study at any time for any reason.

Patients who discontinue from the study should always be asked about the reason(s) for the discontinuation (and informed about their right not to disclose their reason for doing so) and the presence of any adverse events (AEs). If possible, they should always be seen and assessed by an investigator and asked to perform completion outcome measures, including CT, US and QoL questionnaires. A pre-operative CT may be used for follow up should indication to operate the aorta arise. Adverse events should be followed up.

Study treatment should be stopped in the following cases: development of diabetes, persistent renal failure with GFR<45ml/min, severely deteriorating health, aortic surgery or onset of exclusion criteria.

If the study medication is stopped, patients will be asked to remain in the study and follow the other procedures according to the protocol. All randomised patients remain in the group they were originally allocated to for the purpose of intention-to-treat (ITT) analyses.

Patients who discontinue the study will not be replaced.

Sponsor has to be informed if a patient is withdrawn by any reason before study end. The "End of study" form must be filled out by the investigator and the reason should be stated.

The study number will not be reused if a patient is withdrawn.

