5.1.2 Imaging

At baseline, 24 months and completion, the aorta will be examined by non-contrast enhanced CT with 1 mm slices or thinner from the jugulum to the groins.

At enrolment, 24 months and completion the abdominal aorta will be examined by US. The assessment of abdominal aortic diameter with US will be done by the local US technician, using the standardized technique measuring the largest anterior-posterior diameter from leading edge to leading edge perpendicular to the blood flow in the aneurysm. Inclusion criteria will be based on US determined diameter.

If a subject withdraws from the study due to operative need of the aorta, the preoperative CT will be used for analysis in the study. The assessment of aortic diameter on CT will be done using outer edge to outer edge perpendicular to blood flow. Volumetric AAA analysis of CT images will be performed using manual drawing of the vessel wall contours in axial slices of the entire abdominal aortic as well as semiautomatic measures in 3mensio, Pie Medical, Maastricht. Analysis will start at the slice just below the most distal renal artery excluding accessory renal arteries and end at the slice just above the aortic bifurcation. Measures of perivascular adipose tissue will be made adjacent to the aorta.

All CT assessment (diameter and volume) will be done at a core lab at the Department of Radiology, Uppsala university hospital, Uppsala. The CT identification is the four digits enrolment code. The reviewer will be blinded regarding treatment allocation.

CT images will also be reviewed by local radiologists according to GCP at respective hospital. Accidental findings of unrelated pathology on the CT scan will be dealt with as appropriate by investigator at respective site.

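### Sections 2.1 and 5.1.2 treat AAA repair as leaving the study, while 4.2 asks patients who stop study medication to stay; follow-up after repair could therefore differ by site and by arm

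*Combined protocol and SAP*

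**What the plan says.** Section 2.1 defines end of study as completion at 60 months or "discontinuation from study before that for any reason, for example due to AAA repair or patients will". Repair and the patient's own wish are two separate examples.

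Section 5.1.2 takes the same line: "If a subject withdraws from the study due to operative need of the aorta, the preoperative CT will be used for analysis in the study".

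Section 4.2 separates stopping treatment from leaving the study. Its reasons for stopping study treatment include "persistent renal failure with GFR<45ml/min, severely deteriorating health, aortic surgery or onset of exclusion criteria". It then continues: "If the study medication is stopped, patients will be asked to remain in the study and follow the other procedures according to the protocol". Patients who do leave should, if possible, be seen and "asked to perform completion outcome measures, including CT, US and QoL questionnaires", and their adverse events should be followed up.

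Table 1 schedules AE and SAE registration at every contact to 60 months, and the quality-of-life questionnaires at enrolment, 24 months and completion. Section 8.3 names repair, rupture and death as clinical events to be described, and plans a cost-effectiveness analysis from a health-system perspective.

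**The concern.** Nothing ranks these rules. One site can follow 2.1 and 5.1.2 and close the patient at repair. Another can follow 4.2 and keep the patient to 60 months. Seven sites may not choose alike.

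There is also a difference between arms. The stay rule in 4.2 is triggered by stopping study medication. A standard-care patient has none to stop, so on a literal reading only the metformin patient is asked to stay.

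Reaching repair depends on growth, which is what the drug is meant to change. Ending observation at repair is therefore loss related to outcome, and it would be unequal between arms if metformin works. At stake are secondary and safety data: quality of life at the scheduled times, deaths, and adverse events that begin after exit. The primary CT measurement is not the subject here, because a pre-operative CT is provided for.

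**Working it through.** **1. What each rule does to a patient who has AAA repair.**

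| | Metformin | Standard care |
|---|---|---|
| 2.1 | study ends | study ends |
| 5.1.2 | withdraws; pre-operative CT used | withdraws; pre-operative CT used |
| 4.2, stopping list and stay rule | treatment stops; asked to remain | no study medication to stop; rule not triggered |

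For metformin patients the passages contradict each other. For controls 4.2 is silent and only the exit rule applies.

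**2. What is still recorded if the patient leaves at repair.**
- The repair itself.
- One completion set with CT, ultrasound and quality of life, if possible (4.2).
- Adverse events already open. Section 5.2.5 follows these until they cease, or until the patient is under professional care and causality has been assessed. Operations that were not pre-planned count as AEs (5.2.1), and hospitalisation and death are SAE criteria (5.2.3).

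**3. What is lost.** Every later contact in Table 1. For an exit just after the 24-month visit these are the contacts at 30, 36, 42, 48, 54 and 60 months: six occasions for AE/SAE registration and for learning of a death. The 60-month questionnaires are replaced by a set taken around the time of surgery.

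**4. How many patients this could touch (illustration).** The plan gives no figure for this, so there is none to reproduce.

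Inputs from the plan: control growth 3 mm/year, SD 2.17, and a 30% reduction, so 0.7 × 3 = 2.1 mm/year on metformin (8.4); baseline 30–49 mm for men (3.1); repair threshold 55 mm for men (1.1).

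Assumptions: each patient grows linearly, and growth is normally distributed. For baseline b, mean μ and SD σ,

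P(reach 55 mm by 5 years) = 1 − Φ( ((55 − b)/5 − μ)/σ ).

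With σ = 2.17:

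| Baseline | μ = 3 | μ = 2.1 |
|---|---|---|
| 30 mm | (5 − 3)/2.17 = 0.92 → 18% | (5 − 2.1)/2.17 = 1.34 → 9% |
| 40 mm | (3 − 3)/2.17 = 0 → 50% | (3 − 2.1)/2.17 = 0.41 → 34% |
| 49 mm | (1.2 − 3)/2.17 = −0.83 → 80% | (1.2 − 2.1)/2.17 = −0.41 → 66% |

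The documents do not give the baseline distribution. The next table averages the formula over baselines of 30–49 mm, either uniform or skewed to small aneurysms (mean 37 mm), and adds a slower-growth variant.

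| Control growth | Controls | Metformin, each patient's growth × 0.7 | Metformin, mean × 0.7, SD unchanged |
|---|---|---|---|
| mean 3, SD 2.17 | 40–48% | 19–30% | 26–34% |
| mean 2, SD 1.5–2.17 | 18–33% | 5–19% | 10–24% |

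Overall this gives 18–48% of controls and 5–34% of metformin patients. When the two arms share the same assumptions, the control share is higher in every case. The 55 mm threshold was applied to everyone. Women have a 50 mm threshold and enter at 30–44 mm, so they have 6–20 mm to grow, against 6–25 mm for men; the simplification does not inflate the figures.

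**The case against.** The strongest reply is that little goes unrecorded even under 2.1. The exit set includes quality of life, open adverse events are followed, hospitalisation and death are SAE criteria, and the repair is counted. This stands in large part. Perioperative events are at least partly covered, and the loss is confined to what begins or falls due after exit.

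A milder reading is that 2.1 means only patients who choose to leave at repair. That fits poorly: 2.1 lists repair alongside the patient's wish as a separate example, and 5.1.2 gives the operation as the cause of withdrawal.

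Section 8.3 expects repairs, ruptures and deaths to be few. If so, the loss is small. The plan's own growth rate points to many patients reaching threshold, but reaching threshold is not the same as being repaired.

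A reader might infer three stronger things that the documents do not support:
- *A count of missed complications, deaths and repeat operations*, from the rates in section 1.1 (mortality 1–5%, complications up to 20%, repeat surgery about 20%). The share repaired is not given, part of these events would be captured, and the repeat-surgery rate is stated in the setting of life-long follow-up. In the illustration, controls who reach threshold do so at a mean of 3.1–3.9 years, which leaves only 5 − 3.9 = 1.1 to 5 − 3.1 = 1.9 years of the study.
- *That quality of life would be biased against metformin.* No figure for quality of life after repair is given, so the direction is unknown.
- *That the cost-effectiveness analysis fails because of 2.1.* The ratio is cost per procedure avoided, and procedures remain countable. No section describes how costs are collected for any patient, so that gap is not due to 2.1 alone.

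**Conclusion.** The contradiction is real, and the passages must be reconciled for both arms. Read literally, they could keep repaired metformin patients under observation and release repaired controls. What is exposed is later scheduled quality of life, later deaths and new AEs/SAEs, all secondary or safety data.

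The number of patients affected cannot be derived. The 18–48% and 5–34% reaching threshold rest on linear normal growth, an assumed baseline distribution and a single threshold, and they bound the issue only loosely because the proportion repaired is unknown. The sound conclusion is that the loss depends on outcome and would be unequal between arms if metformin works. The change should be made because it is cheap and because data not collected after repair may not be recoverable later.

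**What to change.** - **2.1:** delete AAA repair as an example of end of study.
- **5.1.2:** reword so that repair ends the growth measurement, with the pre-operative CT as the last growth image, but does not end participation.
- **4.2:** state that patients in both arms who undergo repair are asked to remain to 60 months for the contacts already in Table 1, AE/SAE and vital-status recording, and EQ-5D/RAND-36 at 24 and 60 months. The trigger should be the repair, not the stopping of medication, so that the rule reaches standard care.
- **5.2.4:** align it with Table 1. It currently puts completion of AE recording at 24 months.

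This concerns follow-up only and changes no treatment rule. The cost is a wording amendment, with some already planned contacts taking place after repair. Collecting reinterventions and hospital costs would be new work outside the present schedule, and this correction does not depend on it.

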5.1 Study measurements

5.1.1 Clinical data

At the enrolment visit the patients will undergo a clinical examination which consists of; recording of demographic data (date of birth, sex and ethnicity), medical history and concomitant diseases, smoking status, heredity of AAA, current medication, recording of weight & height, heart rate & blood pressure, cardio-pulmonary status and general appearance.

At all points of contact with phone or visit at the clinic any AE and SAE are recorded, target dose of study drug is determined and compliance is asked for. Discontinuation (temporarily or permanent) of study medication ≥ 3 consecutive days will be recorded.

At visits medical events and any changes in smoking status will be noted and vital signs and weight is recorded. Compliance to study drug is noted and remaining tablets are counted. At completion visit and at 24 months, the above plus a physical examination is performed. Changes in current medication are recorded yearly.

At enrolment visit, at 24 months and completion quality of life will be recorded with EQ-5D and RAND -36, see appendix 1.

At enrolment blood samples will be taken for fP-Glc and P-Creatinine, analysed at accredited hospital laboratory. P-Creatinine will be tested for safety every 12 months. A 24 months S-B12 is controlled for possible metformin induced deficiency. In Uppsala and Malmö venous blood samples will be taken at baseline, 24 months and completion for scientific reasons.

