5.2.1 Definition of adverse events

An AE is any unwanted medical occurrence that does not necessarily have to have a causal relationship with the investigational product. An AE can be any unfavourable, unintended clinical sign, symptom, medical complaint or clinically relevant change in laboratory variables or clinical tests. Accidents, operations not pre-planned or deterioration in concurrent illness are also considered as AEs. Known gastrointestinal side-effects of metformin are actively asked for and noted separately.

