8.2.3 Safety variables

Safety variables include differences in drug related AE and GFR.

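### The between-arm safety variable, drug-related AEs, has no usable comparator: control patients take no study drug and, read literally, fall outside the Safety Analysis Set

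*Combined protocol and SAP*

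**What the plan says.** **The variable.** Section 8.2.3 reads: "Safety variables include differences in drug related AE and GFR". Section 8.3 gives no method for comparing AEs between arms.

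**The rating.** Section 5.2.2 asks the investigator to judge whether an AE may be associated with the study drug. Section 2.1 describes the trial as open label, with blinding of outcome assessment only. Under 4.1 the control arm receives standard care, without placebo.

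**The analysis set.** Section 8.1 limits the Safety Analysis Set to patients who have taken study drug at least once.

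**The contacts.** Section 2.1 schedules "one enrolment visit, eight study visits" for everyone, then "ten phone contacts for those randomized to metformin (three to support titration of study drug") and "seven phone contacts for those randomized to standard care". In Table 1 the calls at 2, 4 and 6 weeks carry an asterisk, explained as "For those randomized to metformin only", and the AE and SAE registration rows are marked in those columns. Section 5.1.1 confirms the rule: "At all points of contact with phone or visit at the clinic any AE and SAE are recorded".

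**Gastrointestinal effects.** Section 1.1 states: "Gastro intestinal problems may occur primarily in the run-in phase". Section 5.2.1 adds: "Known gastrointestinal side-effects of metformin are actively asked for and noted separately". It does not say whether this is done in both arms.

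**The concern.** The safety objective in 1.2.4 is to determine adverse events related to metformin. For a drug given for years to people without diabetes, a useful result is how many more events occur than would have occurred anyway. A randomised control arm supplies that background rate, but only if the same events are counted in both arms.

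A drug-related AE is not such an event. It requires a rater to link the event to a drug that controls do not take, and the rater knows who takes it. The control count then says nothing about background. The metformin count mixes true drug effects with background events that an unmasked investigator attributes to the drug. If the safety set also lacks controls, the promised difference has no second term.

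The extra run-in calls raise a separate and smaller question. Even a comparison of all AEs would partly reflect how often patients were asked, in the weeks when gastrointestinal symptoms are expected.

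**Working it through.** **1. Contact counts (Table 1 against 2.1).**
- Calls: 2\*, 3\*, 4\*, 5, 7, 9, 11, 13, 15, 17 = 10. Without the three asterisked calls, 7. This reproduces the 10 and 7 in 2.1.
- Visits: 1, 6, 8, 10, 12, 14, 16 and completion = 8, also as in 2.1.
- AE contacts including enrolment: 1 + 8 + 10 = 19 on metformin, 1 + 8 + 7 = 16 on standard care.
- After baseline: 17 against 14. From baseline to 24 months: 11 against 8.
- First 3 months after baseline: calls 2, 3, 4 and 5 against call 5 alone, so 4 against 1.

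The whole imbalance is three contacts, all within the first 6 weeks. A control's first contact after baseline is the 3-month call.

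**2. The comparator (5.2.2, 4.1, 8.1 and 8.2.3 together).** Causality is rated against the study drug, and controls receive none. A control AE therefore has no drug to be related to, and the expected control count is about 0. This is an inference; no section states it. Separately, a safety set defined by having taken study drug has, on its literal wording, no controls.

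**3. What a near-zero control count does (illustration; the plan names no AE test).** With 250 per arm (2.1) and 0 control events, the two-sided Fisher p for k metformin patients is 2 × C(250,k) / C(500,k).
- k = 5: 2 × (250·249·248·247·246)/(500·499·498·497·496) = 2 × 0.0306 = 0.061.
- k = 6: 2 × 0.0306 × 245/495 = 2 × 0.0152 = 0.030.

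Six rated patients are enough. Suppose metformin has no effect, a share b of patients has a background AE, and a share q of those is rated related. Both shares are assumed; the documents give neither. Expected patients = 250 × b × q, with the probability of 6 or more in brackets:

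| b | q = 5% | q = 10% | q = 20% |
|---|---|---|---|
| 10% | 1.25 (0.002) | 2.5 (0.041) | 5.0 (0.384) |
| 30% | 3.75 (0.176) | 7.5 (0.763) | 15.0 (0.998) |
| 50% | 6.25 (0.596) | 12.5 (0.987) | 25.0 (1.000) |

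With no drug effect at all, the chance of a nominally significant difference runs from negligible to near certain, depending only on rater behaviour and background frequency.

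**4. Unequal run-in ascertainment (illustration; all rates assumed).** With the same true run-in risk p in both arms and capture rates c_M and c_S, the recorded risk ratio is (p × c_M)/(p × c_S) = c_M/c_S.
- c_M = 90%, c_S = 90%: 1.00.
- c_M = 90%, c_S = 70%: 0.9/0.7 = 1.29.
- c_M = 90%, c_S = 50%: 0.9/0.5 = 1.80.

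For p between 10% and 30% and 250 per arm, the chance of a two-sided p below 0.05 is about 13% (p = 10%, c_S = 70%) to 91% (p = 30%, c_S = 50%). With equal capture it is 5%. The documents give no capture rate, so this shows direction, not size.

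**The case against.** A fair defence has several parts.

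- **The data are collected.** AEs of any cause are recorded at every contact in both arms, and the list in 8.2.3 is introduced as inclusive, not exhaustive. An all-AE comparison is therefore possible. This stands, and it is why the repair is cheap. It does not make drug-related AEs a sound between-arm variable.
- **The safety set is probably a drafting slip.** The ITT definition in 8.1 carries the same dose condition, and it can hardly be meant to remove controls from the primary analysis. That is plausible, but the text still needs correcting.
- **The objective can be partly descriptive.** Section 1.2.4 centres on known side effects of metformin, which description of the treated arm can partly serve. Accepted, but 8.2.3 asks for differences.
- **Near zero is not exactly zero.** The category definitions in 5.2.2 refer to study treatment, so a control AE might occasionally be rated related. It would still not be related to the drug.

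A reader might also infer more than the documents support:

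- *That the whole safety comparison is unequal.* It is not. Creatinine is scheduled yearly without restriction by arm (5.1.1, 5.2.9), so neither the calls nor the causality rating touches GFR. That comparison needs only a safety set that contains controls.
- *That control run-in events are lost.* Section 5.1.3 has calls ask about events since the last visit, so these events depend on recall at 3 months.
- *That the extra calls are a mistake.* They support titration, and unmasked rating follows from the open-label design.

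**Conclusion.** The main point holds. As written, 8.2.3 sets metformin against a count that is close to zero by construction, and 8.1, taken literally, removes the comparator altogether. The resulting difference cannot estimate an excess over background. This rests on reading drug-related as related to metformin, which the opening of 5.2.2 supports, and on the literal wording of 8.1.

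The secondary point also holds, within limits. Scheduled AE contacts are 4 against 1 in the first 3 months and equal afterwards. Run-in AEs are therefore ascertained unequally, and a bias towards more recorded AEs on metformin is likely. Its size is unknown because the documents give no rate of recall loss; the ratios of 1.29 to 1.80 are illustrations on assumed rates.

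The primary efficacy analysis is untouched. This is a modest point about safety reporting, worth correcting because the correction is only wording.

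**What to change.** **Section 8.1.** Define the Safety Analysis Set for both arms: metformin patients who took study drug at least once, and randomised standard-care patients.

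**Section 8.2.3.** Compare all AEs, all SAEs and the actively asked gastrointestinal AEs between arms regardless of judged causality. Report drug-related AEs descriptively for metformin only. Keep GFR as it is.

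**Run-in.** Keep the titration calls. Make all AEs from day 0 the main comparison, with a note that run-in ascertainment differed. Add a sensitivity comparison restricted, in both arms, to AEs with onset after the 3-month call.

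Do not restrict instead to AEs registered at contacts common to both arms. A control event from weeks 0 to 6 would be recalled at the 3-month call and counted, while a metformin event from the same weeks would already have been registered at a titration call and dropped. The arms would cover different periods, and the comparison would favour metformin in the window where gastrointestinal effects are expected.

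**Cost.** Wording and a little more tabulation, from AE data already collected. The sensitivity comparison omits the run-in window, so it supplements the main one and cannot replace it. It also assumes that the eCRF records AE onset date, which the documents do not state and the sponsor should confirm.
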